
these cases the residual proteinuria may be explained by the residual kidney scars rather than the persistence of the immunologic disease.⁴²

[figure not shown]

Figure 3. Representative plots of anti-PLA2R (gray squares) and proteinuria (black diamonds) versus time following initial RTX treatment. Values are plotted as percent of baseline value. Panel A and B depicts the typical reduction and disappearance of anti-PLA2R followed by resolution of proteinuria exhibited by the majority of patients. Panel C is representative of patients in whom anti-PLA2R did not substantially decline following treatment and the associated with persistence of proteinuria. Panel D depicts the single patient whose anti-PLA2R level returned with relapse of his disease after having initially disappeared.

This incomplete mirroring of immunological improvement by clinical status is an important issue. As mentioned, proteinuria could remain at a sub-nephrotic level in spite of the absence of immunological disease activity. In this situation, further immunosuppression would have no benefit but would have continued toxicity risk. In contrast, at a similar level of proteinuria, immunological activity, as detected by the continuing presence of circulating anti-PLA2R could be ongoing. In this setting, an increase or change in immunosuppressive regimen may be the best strategy. Ultimately, if confirmed anti-PLA2R levels may become an important surrogate assessment of disease activity and of treatment outcome. We propose to expand these observations by measuring anti-PLA2R levels in all patients enrolled into the current trial. This in itself will be a major innovation for the results of these studies have the potential to create a new paradigm for monitoring and treatment in patients with IMN. If confirmed, the

autoantibody level can be added to predictive algorithms and have the potential to influence future treatment protocols and lead to improved care of patients with IMN.

OVERALL RESEARCH DESIGN AND METHODS:

The goal of this proposal is to conduct a prospective randomized controlled phase III study comparing Rituximab (RTX) to Cyclosporine (CSA) in the treatment of patients with IMN. Once a patient with IMN and proteinuria $\geq 5\text{g}/24\text{h}$ is identified, meets other entry criteria and consents to the study, he/she will receive a minimum of 3 months of conservative therapy aimed at maximizing Angiotensin II blockade (run-in phase). If at the end of this period the patient still meets entry criteria he/she will be randomized into a 12-month treatment period, and a subsequent follow-up of 12 months. Efficacy of treatment will be assessed by remission status (based on changes in proteinuria) at 24 months from randomization. Patient safety will be assessed via collection of adverse event data and evaluation of pre- and post-treatment laboratory data. At the 6-month post-randomization visit, patients who have been randomized to either CSA or RTX but who do not have a reduction in proteinuria $\geq 25\%$ (confirmed on repeat measurements within 2 weeks) will be considered treatment failures and exit the study. Data from that point onward will be censored. Patients in the RTX group who have a reduction in proteinuria of equal to or $>25\%$ at 6 months will be given another identical course of RTX (1g x 2). This treatment regimen was chosen given our initial data that suggested a percentage of our cohort appeared to respond to an additional course of therapy. Data from our 2 pilot studies showed that RTX is out of the circulation by month 2 in the majority of patients and B cells have recovered by month 3 in patients treated with RTX 1g x 2 (the regimen chosen for the study). Thus, at 6 months, patients in the RTX arm are completely, at least as best as we can measure, free of immunosuppression, and hence the second course should not be associated with additive toxicity. The same definition of response will apply to the CSA arm at 6 months. An equal to or $>25\%$ reduction in proteinuria will dictate continuation of the CSA for an additional 6 months (total of 12 months of full dose CSA). This assessment at six months allows a balance between risk-benefit in both arms. The protocol provides similar exposure to immunosuppression in both arms and allows an early exit for patients related to safety issues by providing a lack of efficacy (futility) end point at 6 months.

Primary endpoint

CR or PR (defined as per table 1) at 24 months after randomization will be the primary endpoint. This will be assessed in an intention to treat (ITT) analysis.

Secondary endpoints

1. Relapse state at month 24 after randomization (Urine Protein (UP) $> 3.5\text{ g}/24\text{h}$ after earlier CR or PR)
2. Anti-PLA2R levels
3. Quality of life as measured by modified KDQOL
4. Adverse events

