5. ESRD
6. CR or PR, and CR alone at 6, 12, 18, and 24 months after randomization
7. Time to CR or PR
8. Effect of treatment on renal function, as assessed by slope of creatinine clearance from baseline to 24 months.

Table 1. Definition of remission status

Remission status	Proteinuria (UP g/24 hours) after treatment
Complete remission (CR)	UP \leq 0.3 g/24h and serum albumin \geq 3.5g/dl
Partial remission (PR)	Reduction in baseline UP of \geq 50% plus final UP \leq 3.5 g/24h but $>$ 0.3 g/24h
Non-response (NR)	Reduction in baseline UP of $<$ 25% (includes increase in UP)
Relapse	Development of nephrotic range proteinuria following CR or PR, i.e. $>$ 3.5g/24h

Patient recruitment

The study population will be comprised of individuals with biopsy-proven idiopathic MN. Total study size will be 126 patients, enrolled among up to 25 participating sites. Potential candidates for the study will be identified by the investigators using existing databases and clinical trial networks. The P.I. or the study coordinator will contact these potential candidates and if the preliminary interview indicates their willingness to participate, a consent form will be reviewed with the patient. If a potential candidate remains interested, the consent form will be signed, and the patient enrolled in the study. The institutional review board at each participating site will approve the recruitment process and consent forms. The Mayo Nephrology Collaborative Group (MNCG) will post information on its web site describing the study and identifying local contacts at the collaborating centers. Each site involved may have their own methods of informing and recruiting potentially eligible patients but in all cases will have IRB approval before embarking on this process. Each site will be expected to randomize approximately 6-10 patients over the recruitment period. If, based on site estimates of the IMN population that would be eligible for this study, we enroll approximately 30% of the annual population in a single year our recruitment will be complete. We have assembled a consortium for this trial with a population that well exceeds the enrollment needs based upon the multi-year enrollment plan for this trial.

Recruitment strategy

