Adverse events (both patient and event counts) will be tabulated by body system, severity and, for each severity, by investigator-assessed relationship to study drug. Group comparisons for adverse events with 4 or more occurrences will be done using chi-square or Fisher's exact test. The last RTX injection is at 6 months and the tapering of Cyclosporine will be completed by the end of month 14. Hence, the adverse events analyses will focus on events through month 18, allowing these additional months for potential lingering Cyclosporine or RTX complications.

The analysis of the primary endpoint (urine protein failure at month 24) will be intent-to-treat (ITT), and will include all randomized subjects in the analysis. For those without a 24 month visit, the 18 month visit results will be used if available, otherwise they will be assumed to have failed at 24 months. Per protocol (PP) analyses will also be done including only those subjects who receive a full course of study medication and who have a 24 month visit.

Interim analyses: No interim analyses for efficacy will be performed during the trial, however safety data will be compiled and reviewed approximately every six months or at the request of the Data and Safety Monitoring Board.

Investigator and Coordinator Training: In order to make efficient use of funding, annual investigator and coordinator meetings will be coordinated with national nephrology meetings where possible. It is expected that the majority of the training will occur through web-based technology and will be coordinated through the data management and coordinating Center.

The **Data Management and Coordinating Center (DMCC)** is located at the Applied Health Research Center (AHRC) at St. Michael's Hospital/University of Toronto. The DMCC will be responsible for facilitating all aspects of the study planning, training, implementation, data collection and analysis.

The clinical information collected for this study will be stored at the DMCC at the Applied Health Research Centre of St. Michael's Hospital in Toronto, ON, Canada and also sent to a federal data repository held by the Office of Rare Diseases Research (ORDR) and located at the University of South Florida (USF) in Tampa, FL.

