An unexpected adverse event is defined as any adverse experience...the specificity or severity of which is not consistent with the risks of information described in the protocol or product monograph.

Expected adverse events are those that are identified in the research protocol or product monograph as having been previously associated with or having the potential to arise as a consequence of participation in the study.

All adverse events that occur between Time 0 and study termination will be reported. All reported adverse events will be classified using the current version of the Common Terminology Criteria for Adverse Events (CTCAE) developed and maintained by CTEP at National Cancer Institute.

- Within **24 hours** (of learning of the event), investigators must report any Serious Adverse Event (SAE) that:
 - Is considered life-threatening/disabling or results in death of subject
 - OR-
 - Is Unexpected/Unanticipated
- Investigators must report all other SAEs within **5 working days** (of learning of the event).
- All other AEs must be reported to the DMCC within **20 working days** of the notification of the event or of the site becoming aware of the event.

Local institutional reporting requirements to IRBs, any GCRC oversight committee and the FDA, if appropriate, remain the responsibility of the treating physician.

As part of the reporting structure, SAEs will be reported to Health Canada, Genentech Drug Safety and the Genentech medical science liaison. An adverse event summary form will be completed and will be summarized for each IRB and Health Canada annually.

Sites will enter all Adverse Event data into the study eCRF. Upon entry of a serious adverse event, the system will notify the DMCC by email. The DMCC will in turn notify the study PIs, the designated medical monitor and any other designated personnel by email. The medical monitor will then review the SAE data to determine causality (definitely not related, probably not related, possibly related, probably related, definitely

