related) of the serious adverse event. The medical monitor [and, if applicable, sponsor] may request further information if necessary and possibly request changes to the protocol or consent form as a consequence of the serious adverse event. A back-up notification system is in place so that any delays in review by the medical monitor beyond a specified period of time are forwarded to a secondary reviewer. The eCRF maintains audit trails and stores data (and data updated) related to any adverse event in the study.

Study Discontinuation

The Study Sponsor, DSMB and local IRBs (at their local site) have the authority to stop or suspend this trial at any time. This study may be suspended or closed if:

- Accrual has been met
- The study objectives have been met
- The Study Investigators believe it is not safe for the study to continue
- The DSMB suspends or closes the trial

Subject Discontinuation

An intent to treat approach will be used. All data acquired prior to termination for the reasons outlined below will be included in the primary analysis unless patient withdraws consent. Every effort will be made to conduct a final study visit with the participant and participants will be followed clinically until, if applicable, all adverse events resolve.

Reasons for subject discontinuation include:

- Withdrawal of consent
- Withdrawal by the participant
- Withdrawal by the investigator
- Intercurrent illness or event that precludes further visits to the study site

Regulatory issues:

1. Inclusion of women: Women make up approximately 30-50% of the population of patients with IMN and are expected to be enrolled in numbers in proportion to this normal distribution.
2. Inclusion of minorities: Individuals of all races and ethnicities are at risk for MN. Based on the ethnic composition of the patients followed at, and referred to the Mayo Clinic the population served will include African-Americans, Asian, and Hispanic subjects proportional to that in the general US and Canadian population. This will ensure adequate enrollment within the different racial groups.

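### Censoring month-6 treatment failures, if applied literally, overstates remission in time to CR/PR, at months 12 and 18 and in the GEE; the primary is not affected

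*Combined protocol and SAP*

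**What the plan says.** Overall Research Design and Methods states the month-6 rule for both arms: patients without a confirmed proteinuria reduction of at least 25% "will be considered treatment failures and exit the study. Data from that point onward will be censored". The Rituximab and Cyclosporine paragraphs repeat that these patients leave the study as failures of therapy and do not mention censoring. Patient monitoring and evaluation confirms that the month-6 visit is their last.

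For the primary endpoint, CR or PR at month 24, the plan says "This will be assessed in an intention to treat (ITT) analysis". The Statistical and Analytical Plan uses the month-18 result when month 24 is missing; without either, patients are scored by the rule "otherwise they will be assumed to have failed at 24 months". Under Subject Discontinuation, data acquired before termination "will be included in the primary analysis unless patient withdraws consent".

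The secondary endpoints include "CR or PR, and CR alone at 6, 12, 18, and 24 months after randomization" and "Time to CR or PR". Chi-square tests, logistic regression and GEE models are planned for remission by visit. No denominator is stated for patients who left at month 6. No estimator or censoring rule is stated for time to CR or PR.

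**The concern.** The month-6 rule does two things in succession: it labels the patients failures, then censors them. In a time-to-event analysis these conflict. A failure is known not to have remitted on study treatment. A censored patient is assumed to have the same future chance of remission as those still under observation. Here the patient is removed because the response was poor, so that assumption fails by design.

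At stake are the secondary remission results: time to CR/PR, remission at months 12 and 18, and the longitudinal comparison. Specific Aim 3 concerns remission during active treatment, and the protocol defines the first 12 months as the treatment period, so month 12 and time to remission bear directly on that aim. The trial is open-label, which is a further reason to fix the rule before the data are seen.

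**Working it through.** **What is not affected.** The planned sample size reproduces. With 55% v 45%, a margin of 15 points and one-sided alpha 0.025 (Sample size estimation), n = (1.960 + 0.842)² × (0.55×0.45 + 0.45×0.55) / (0.10 + 0.15)² = 62.2, so 63 per arm as stated (power 80.5%). Month-6 exiters have no month-18 or month-24 visit and are therefore already failures in the primary. A patient who fails CR/PR at month 24 cannot be in CR, so CR alone at month 24 follows. Month-6 remission is observed before exit.

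**What no passage settles.** The assumed-failed rule is written for the primary. The non-responder rule in Sample size estimation concerns patients lost to follow-up, not exits required by the protocol. The general ITT sentence under Subject Discontinuation says who is analysed, not how status after exit is scored: a Kaplan-Meier curve over all randomised with exit censored could still be called ITT.

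**Inputs for the illustration.** True remission of 55% borrows the plan's month-24 rate for rituximab. Exit rates e of 10% and 20% are assumptions. True means that an exiter counts as not in remission, as the failure labels say.

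**1. Exiters dropped at months 12 and 18.** Shown rate = p / (1 − e).
- e = 10%: 0.55 / 0.90 = 61.1%
- e = 20%: 0.55 / 0.80 = 68.8%

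**2. Kaplan-Meier with exit censored at month 6.** Let a remit by month 6 and b later, with a + b = 0.55. Shown rate = 1 − (1 − a) × [1 − b / (1 − a − e)].

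| a | b | e = 10% | e = 20% |
|---|---|---|---|
| 0.10 | 0.45 | 60.6% | 67.9% |
| 0.20 | 0.35 | 60.0% | 66.7% |
| 0.40 | 0.15 | 58.0% | 62.5% |

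Worked case, a = 0.20, e = 20%: 1 − 0.80 × (1 − 0.35/0.60) = 66.7%. With exit as a competing event, cumulative incidence is a + b = 55% in every cell.

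**3. GEE without rows after exit.** This was simulated with 20% exit and true remission of 60%, 58% and 50% at months 12, 18 and 24. An independence working correlation gave 75.0%, 72.6% and 62.3%. An exchangeable one gave 69.9%, 67.4% and 56.8%.

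**4. Between arms, exiters dropped.**
- True 55% in both arms, equal exit: no false difference.
- True 55% in both arms, exit 20% v 10%: 68.8% − 61.1% = 7.6 points in favour of the arm with more exits. Swapping the exit rates reverses the sign.
- True 55% v 45%, exit 20% in both: 68.75% − 56.25% = 12.5 points, against a true 10.0.
- True 55% v 45%, exit 18% v 20%: 0.55/0.82 − 0.45/0.80 = 67.1% − 56.3% = 10.8 points. The bias favours the arm with fewer exits.
- 68.75% of stayers remit in both arms, exit 20% v 10%: true 55.0% v 61.9%, so a real 6.9 points is shown as zero.

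**The case against.** The strongest reply is that the biased reading is not one the plan adopts. The censoring sentence directly follows the failure label, and both treatment paragraphs repeat that label. The analysis plan uses the same verb for renal function readings at dialysis or transplant, where it can simply mean that later readings are not used. Read that way, the month-6 rule says failure plus no later data, and there is no overstatement once exiters are scored as non-remitters. This stands as a limit: the defect is an unstated or ambiguous rule. It does not remove the point, because time to CR/PR has no other censoring instruction.

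A second reply is that the true rate here is a definition. The protocol notes that proteinuria falls gradually over months, so some exiters might remit later, unobserved. That also stands. The overstatement is measured against a composite outcome in which exit is failure. Against remission regardless of later therapy, it cannot be checked.

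Third, the exit rates are assumed. The nearest figure, five non-responders among the 14 pilot patients who completed 12 months, is not a month-6 exit rate under the 25% rule.

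Stronger readings that a reader might infer are not supported:
- **The non-inferiority result is compromised.** It is not; the primary already scores these patients as failures.
- **The comparison always leans towards the arm with more exits.** The 18% v 20% example shows otherwise. The statement holds when the true rates are equal and, for Kaplan-Meier, when the timing of remission is also the same.
- **Safety data are cut off at exit.** The adverse event section says "All adverse events that occur between Time 0 and study termination will be reported", and under Subject Discontinuation "participants will be followed clinically until, if applicable, all adverse events resolve".

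**Conclusion.** The concern holds in a conditional form. If the censoring sentence is applied literally to time to CR/PR, or used to drop month-6 failures from months 12 and 18 or from the GEE, remission within each arm is overstated. At a true 55%, the excess from dropping exiters is 6.1 points at 10% exit and 13.8 at 20% (61.1 − 55 and 68.75 − 55). By Kaplan-Meier it is 3.0 to 5.6 points and 7.5 to 12.9 points. These sizes rest on assumed exit rates and on counting exit as failure. The direction between arms is unknown, since it depends on both the exit rates and the true rates. The primary, the sample size, CR alone at month 24 and month-6 remission are unaffected. This should be corrected as a matter of secondary-endpoint specification; it is not a threat to the main conclusion.

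**What to change.** In Overall Research Design and Methods, replace the censoring sentence with: *Month-6 treatment failures count as not in remission at all later visits in all remission analyses; proteinuria after exit is not used for these analyses.* Leave ESRD and safety data collection and reporting as they are.

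In the Statistical and Analytical Plan, add:

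1. Month-6 failures stay in the denominator as non-remitters at months 12 and 18 and in the GEE.
2. Time to CR or PR is analysed over all randomised patients by cumulative incidence, with month-6 treatment failure without earlier CR or PR as a competing event, not as censoring.
3. The number of month-6 exits is reported by arm.

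Keeping exiters event-free in the Kaplan-Meier risk set is not an equivalent to item 2 once other patients are lost. Suppose 20% remit by month 6, 20% exit, and a random 20% of the remaining 60% are lost before the later remissions. The later remissions seen are then 0.35 × 0.80 = 0.28, among 0.48 still observed. The competing-event estimate is 0.20 + 0.60 × 0.28/0.48 = 55.0%. With exiters kept in the risk set it is 1 − 0.80 × (1 − 0.28/0.68) = 52.9%.

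The cost is wording only, with no change to visits, treatment or follow-up. Reported secondary remission rates will be lower than under censoring, and any late remission after exit will count as non-remission. That composite definition should be stated openly.

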5. ESRD
6. CR or PR, and CR alone at 6, 12, 18, and 24 months after randomization
7. Time to CR or PR
8. Effect of treatment on renal function, as assessed by slope of creatinine clearance from baseline to 24 months.

Table 1. Definition of remission status

Remission status	Proteinuria (UP g/24 hours) after treatment
Complete remission (CR)	UP \leq 0.3 g/24h and serum albumin \geq 3.5g/dl
Partial remission (PR)	Reduction in baseline UP of \geq 50% plus final UP \leq 3.5 g/24h but $>$ 0.3 g/24h
Non-response (NR)	Reduction in baseline UP of $<$ 25% (includes increase in UP)
Relapse	Development of nephrotic range proteinuria following CR or PR, i.e. $>$ 3.5g/24h

Patient recruitment

The study population will be comprised of individuals with biopsy-proven idiopathic MN. Total study size will be 126 patients, enrolled among up to 25 participating sites. Potential candidates for the study will be identified by the investigators using existing databases and clinical trial networks. The P.I. or the study coordinator will contact these potential candidates and if the preliminary interview indicates their willingness to participate, a consent form will be reviewed with the patient. If a potential candidate remains interested, the consent form will be signed, and the patient enrolled in the study. The institutional review board at each participating site will approve the recruitment process and consent forms. The Mayo Nephrology Collaborative Group (MNCG) will post information on its web site describing the study and identifying local contacts at the collaborating centers. Each site involved may have their own methods of informing and recruiting potentially eligible patients but in all cases will have IRB approval before embarking on this process. Each site will be expected to randomize approximately 6-10 patients over the recruitment period. If, based on site estimates of the IMN population that would be eligible for this study, we enroll approximately 30% of the annual population in a single year our recruitment will be complete. We have assembled a consortium for this trial with a population that well exceeds the enrollment needs based upon the multi-year enrollment plan for this trial.

Recruitment strategy

Potential candidates for the study will be identified by the P.I. at each site using existing research and clinical databases and clinical trial networks. With local IRB approval, electronic health records and pathology clinical data bases will be used for cohort discovery at each institution. Study investigators will also contact local research volunteer registries and local patient advocacy groups and request they provide information about this trial to their participants/members. Each participating site will be encouraged to accept referrals of study patients identified from national patient volunteer registries such as researchmatch.org and the Office of Rare Disease Research sponsored patient contact registry. Regional advertising will also be carried out via our ongoing participation in the NEPTUNE trial (sponsored by the NIDDK/ODR.) through its collaborative network of 18 academic centers in North America. The P.I. or the study coordinator will contact potential study candidates and if the preliminary interview indicates their willingness to participate, a consent form will be reviewed with the patient. If a potential candidate remains interested, the consent form will be signed, and the patient enrolled in the study. According to our site estimates, only 18% of the available population will need to be eligible and willing to participate in the trial to achieve the target sample size.

Potential Challenges and Solutions

Patient recruitment is often slower than anticipated in clinical studies. The team of clinical centers engaged in this trial, including the primary Mayo Clinic site, has significant experience in recruitment and conduct of clinical trials. Past recruitment success at Mayo into phase I and II trials of RTX in adults with MN is documented by the enrollment of 15 patients in less than 6 months and 20 patients in 11 months.^{71, 75} At Mayo Clinic alone, an average of 50 cases of MN a year have been diagnosed for the past 5 years based on kidney biopsy registry. The projected available population is > 200% of the recruitment goal.

If enrollment at some of the involved clinical sites is slower than expected, we have the option to recruit additional patients from the other participating sites or add, for example, additional sites from the Neptune Consortium to our trial.

Inclusion Criteria

- Idiopathic MN diagnosed by renal biopsy (original biopsy needs to include light, immunofluorescence and electron microscopy); pathology report must be adjudicated by a study PI ([name] or [name], or documented delegate) prior to randomization.
- Age 18-80 years inclusive
- If female, must be post-menopausal, surgically sterile or practicing a medically approved method of contraception (with exception of no birth-control pill given the potential for increased risk of thromboembolism in the nephrotic setting).
- Patient must be off prednisone or mycophenolate mofetil for >1 month and alkylating agents for >6 months. The rationale is to minimize the potential confounding effect of delayed benefits from previous immunosuppressive agents and to reduce the risk of too much immunosuppression from the combined previous drug exposure plus trial drug exposure, e.g. infections.
- Treatment with an ACEi and/or ARB, for ≥3 months prior to randomization and adequate blood pressure control (target BP is <130/80 mm Hg in >75% of the readings, but subjects with BP <140/80 mmHg in >75% of the readings will be eligible).

OR

If patient is intolerant to even a very low dose of either ACEi or ARB therapy, approval for participation in the trial has been obtained from the study PI(s) prior to randomization.

Patients with documented evidence of ≥3 months treatment with maximal angiotensin II blockade, on an HMG-CoA reductase inhibitor, and BP control (BP <140/80 mm Hg in >75% of the readings) who remain with proteinuria ≥5g/24h and meet the other eligibility criteria (as confirmed at the Time 0 visit by the central lab results) may enter the treatment phase of the study and be randomized to RTX/CSA without the need of the run-in/conservative phase of the study. However, in addition these patients must have a documented <50% reduction in proteinuria compared to previous 24 hr proteinuria or Uprot/Ucrea ratio estimates during this period of ACEi and/or ARB treatment otherwise they must fulfill the run-in requirement.

- (Please refer to manual of operation for clarification of tests mandated for patients who are randomized without the run-in period)

- Proteinuria $\geq 5\text{g}/24\text{h}$ using the average from two 24-hour urine collections collected within 14 days of each other despite Ang II blockade for ≥ 3 months as described above.
- Estimated GFR $\geq 40 \text{ ml/min}/1.73\text{m}^2$ while taking ACEi/ARB therapy OR quantified endogenous creatinine clearance $\geq 40 \text{ ml/min}$ based on a 24 hour urine collection. The GFR will be estimated using the 4 variable MDRD equation as published in the NKF-CKD guidelines.⁸¹ This approach is adopted, rather than the much more expensive and more invasive techniques (e.g. inulin or iothalamate clearance) since the likelihood of detecting significant changes in GFR in this short term study is remote regardless of which method is chosen. At entry into the study and at set time points thereafter patients will also have a 24h urine collection for calculation of CrCl and proteinuria.

Exclusion Criteria

- Patients with presence of active infection or a secondary cause of IMN (e.g. hepatitis B, SLE, medications, malignancies). Testing for HIV, Hepatitis B and C should have occurred < 2 years prior to enrollment into the study. Screening for malignancy should be carried out according to standard guideline recommendations.
- Type 1 or 2 diabetes mellitus: to exclude proteinuria secondary to diabetic nephropathy. Patients who have recent history of steroid induced diabetes but no evidence on renal biopsy performed within 6 months of entry into the study are eligible for enrollment.
- Pregnancy or breast feeding (for safety reasons).
- History of resistance to CSA (or other calcineurin inhibitors, e.g. tacrolimus), RTX or alkylating agents (e.g. Cytoxan). Patients who previously responded to CSA/CNI, RTX or alkylating agents with either a CR or PR but relapsed off CSA/CNI after 3 months, or relapsed off RTX or alkylating agent after 6 months, are eligible.

Randomized Treatment Groups: Once all entry criteria have been satisfied and confirmed, patients will be randomized to treatment with Rituximab or Cyclosporine. Randomization will be performed by study site staff through the electronic case report form (eCRF.) The randomization list will be stratified by site, and generated by the Data Management and Coordinating Center (DMCC) using random permuted blocks of variable size.

Rituximab: Patients randomized to the RTX arm will receive 1000 mg IV on Days 1 and 15. Patients who achieve complete remission at 6 months will not be retreated. A second course of RTX 1000 mg IV will be administered at study month 6 for individuals who have not achieved a complete remission, but have achieved at least a $\geq 25\%$ reduction compared to their central laboratory (Mayo Clinic Rochester) baseline (Time 0) proteinuria (but not a CR). Dosing at study month 6 will be independent of CD19/20+ B cell count. The rationale for retreating patients who have had an equal to or $> 25\%$ reduction in proteinuria at 6 months is based on our experience in our pilot studies (first study using 1000 mg on Days 1 and 15 and second study using 4 weekly doses of $375\text{mg}/\text{m}^2$) where an increase in the proteinuria remission rate was achieved after a second course of treatment. In our 2 studies repeated courses of RTX were not associated with additive adverse effects in comparison to their first course. If after six months the reduction in proteinuria is less than 25% compared to baseline the RTX treatment will not be repeated, the patient will exit from the study and will be considered a failure of therapy.

Dosage and Administration of Rituximab: The first infusion of both courses (Day 1 and Day 181) of RTX will be administered IV at an initial rate of 50 mg/hr. All patients

will be premedicated with acetaminophen (1g) and diphenhydramine HCl (50 mg) by mouth from 30 to 60 minutes prior to the start of an infusion. Premedication with steroids (100 mg methylprednisolone IV) will also be given 30 minutes prior to the first infusion of each series of RTX (Day 1 and Day 181). If a hypersensitivity or infusion-related reaction does not occur, the infusion rate will be escalated by 50 mg/hr increments every 30 minutes, to a maximum of 400 mg/hr. If a hypersensitivity (non-IgE-mediated) or infusion-related reaction develops, the infusion will be temporarily slowed or interrupted. Treatment of infusion-related symptoms with additional diphenhydramine and acetaminophen will be recommended. Additional treatment with bronchodilators or IV saline may be indicated. The infusion may be continued at one-half the previous infusion rate upon improvement of the patient's symptoms. If the infusion was well tolerated, subsequent infusions (Day 15 and Day 195) may be administered at an initial rate of 100 mg/hr and increased by 100 mg/hr increments at 30-minute intervals, to a maximum of 400 mg/hr as tolerated. If the first infusion was not tolerated, the guidelines for the first infusion should be followed for all subsequent infusions. Patients administered an antihistamine for treatment or prevention of infusion related reactions will be given appropriate warnings about drowsiness and impairment of driving ability prior to discharge. Participants will be observed for 1 hour post infusion.

Although most study visits have a window of +/- 10 days, the 2nd infusion in each series (i.e., Day 15 and Day 195) will have a more restricted window of +/- 3 days. Specifically, the 2nd infusion in each series should occur 14 days +/- 3 days from the time of the 1st infusion in the series. The window is to account for weekends, holidays, and scheduling conflicts.

Monitoring of Rituximab Effects

The numbers of CD19/20+ B cells in the peripheral blood will be quantified by flow cytometry using peripheral blood leukocytes. Flow cytometry will be performed pre-RTX treatment and at regular intervals following administration of RTX (see Table 2b: Test Schedule and Monitoring for Rituximab Treatment Arm). These assays will allow us to follow the level of B-cell depletion, kinetics of B-cell reconstitution and the composition of cells that re-populate the B-cell pool after treatment with RTX as well as helping to ensure dosing adequacy in these patients.

Cyclosporine: Neoral brand (Novartis) is the preferred Cyclosporine product for this trial. Participating sites must contact the DMCC *prior* to dispensing any other brand to study participants as not all brands of Cyclosporine are bio-equivalent. Patients randomized to the Cyclosporine arm will be started at a dose of CSA = 3.5 mg/kg/day p.o. divided into 2 equal doses given at 12 hour intervals. Target trough CSA blood levels, as determined in whole blood by HPLC, are 125 to 175 ng/ml. Patients will have their doses adjusted according to their blood levels of CSA as monitored every 2 weeks +/- 3 days until the target trough level is reached. After reaching target, CSA trough levels will continue to be checked as per the visit schedule (Table 2a). If a complete remission is achieved by six months, CSA will be tapered by approximately 1/3 of the maintenance dose monthly and hence discontinued after two months. If there has been at least an equal to or >25% reduction compared to their central laboratory (Mayo Clinic Rochester) baseline (Time 0) proteinuria (but not complete remission) the CSA will be continued for an additional six months. A persistent and otherwise unexplained increase in serum creatinine >30% will prompt an approximate 25% dose reduction of CSA, aiming for a corresponding 25% reduction in CSA trough level (for example, if trough

CSA was 175 ng/ml the goal would be to reduce it to 130 ng/ml by reducing the dose by approximately 25% - dose reduction is approximate because CSA is only available in specific dose strengths (25mg, 100mg) and therefore some rounding may be required). If with this dose reduction the creatinine does not return to within 30% of baseline levels within 3 weeks, then a second dose reduction of approximately 25% with a similar reduction in CSA trough level (e.g. if CSA trough level was 100 ng/ml, reduce to 75 ng/ml) will be used. If the creatinine does not fall to within 30% of baseline values with this second dose reduction, the drug will be discontinued. If after six months the reduction in proteinuria is less than 25% compared to baseline the drug will be discontinued, the patient will exit from the study and be considered a failure of therapy. At the end of 12 months, Cyclosporine will be tapered by 1/3 of the maintenance dose monthly and hence discontinued after 2 months. Serum potassium and serum creatinine levels will be checked at the initiation of Cyclosporine in conjunction with blood draw for CSA level. If Cyclosporine dose is changed during treatment, potassium, creatinine and CSA levels will be rechecked every two weeks +/- 3 days post increase/decrease in CSA dosage until levels are stable and at target.

[figure not shown]

Figure 4. Schematic representation of the study design.

Blinding

This will be an open-label study with neither patients nor physicians blinded. Blinding, for this study, was considered difficult and unnecessary and would significantly add to the cost of the study. The need to provide RTX intravenously would require that the CSA arm patients would have to receive an IV infusion of saline which seems unjustifiable from the scientific and budgetary points of view. Furthermore, with the exception of

quality of life measures, all endpoints are based on objective (laboratory) criteria. Having the physicians in the study blinded to CSA level also introduces a potential risk factor that's unnecessary in our estimation. Documentation of cyclosporine levels will ensure that patients are taking the drug at the appropriate time and achieving the prescribed levels indicated in the protocol.

Pharmaceutical logistics

